10.3.5 Analysis of PK variables

For all PK analyses, the Pharmacokinetic Analysis Set will be employed.

- Plasma concentrations of selexipag and ACT-333679 will be summarized per time point by dose and period using arithmetic mean, geometric mean, minimum, median,

maximum, standard deviation (SD), standard error (SE), and two-sided 95% CI of the means.

- $C_{trough, ss}$ of selexipag and ACT-333679 will be listed by dose, period and subject, and will be summarized by dose and period using arithmetic mean, geometric mean, minimum, median, maximum, SD, SE, and coefficients of variation (CV, CV_{ln}) in %, and two-sided 95% CI of the means.
- $C_{max, ss}$, $t_{max, ss}$, and $AUC_{\tau, ss}$ of selexipag and ACT-333679 will be listed by dose, period, and subject.
- $C_{max, ss}$, $t_{max, ss}^*$ and $AUC_{\tau, ss}$, will be summarized by dose and period with arithmetic mean, geometric mean, minimum, median, maximum, SD, SE, $CV\%$ and $CV_{ln}\%$, 95% CI of the arithmetic and geometric means, and inter-subject coefficient of variation (CV_b). (* For $t_{max, ss}$, the geometric mean, its 95% CI and CV_{ln} will not be calculated).
- Differences in $C_{max, ss}$ and $AUC_{\tau, ss}$ of selexipag and ACT-333679 between periods will be explored after dose normalization and within each dose level by using the 90% CI of the ratio of the geometric means of selexipag i.v. (test treatment) versus selexipag oral (reference treatment). The log-transformed values will be analyzed by mixed-effect models including treatment and period as fixed effects and subject as random effect. The ratios of geometric means and their 90% CI will be calculated from the corresponding back log-transformed contrasts of the mixed-effects models for $C_{max, ss}$ and $AUC_{\tau, ss}$ of selexipag and ACT-333679 after oral or i.v. selexipag administration.
- Differences for $t_{max, ss}$ of ACT-333679 between periods will be explored within each dose level using the Wilcoxon signed rank test providing the median differences and their 90% CI.
- Dose proportionality for $AUC_{\tau, ss}$ of selexipag and ACT-333679 after selexipag i.v. will be explored by the power model as described by [Gough 1995], (this analysis will only be done if there are at least 3 different doses in the study).
- $C_{max, ss}$ and $AUC_{\tau, ss}$ ratio of ACT-333679 / selexipag will be listed by dose, period, and subject and will be summarized by dose and period.

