Table 12	QT prolongations in ECG parameters	33
Table 13	Analysis visit windows.....	42
Table 14	Thresholds for marked laboratory abnormalities	65

LIST OF FIGURES

Figure 1	Study design and flow	10
----------	-----------------------------	----

LIST OF APPENDICES

Appendix A	Protocol synopsis.....	58
Appendix B	Visit and assessment schedule.....	63
Appendix C	Discussion and further considerations of the applied statistical methods	65
Appendix D	Definitions of marked abnormalities and elevated liver function tests	65
Appendix E	Mock layout.....	66
Appendix F	Document history	135

LIST OF ABBREVIATIONS AND ACRONYMS

AE	Adverse event
ADaM	Analysis data model
ALT	Alanine aminotransferase
AP	Alkaline phosphatase
AST	Aspartate aminotransferase
ATC	Anatomic Therapeutic Chemical
AUC _{τ, ss}	Area under the plasma concentration-time curve during a dose interval at steady state
b.i.d.	Twice daily
BLQ	Below limit of quantification
CDISC	Clinical data interchange consortium
CI	Confidence interval
C _{max, ss}	Maximum plasma concentration at steady state
CSR	Clinical study report
C _{trough, ss}	Trough plasma concentration at steady state
CV	Coefficient of variation
CV _b	Inter-subject coefficient of variation
DBP	Diastolic blood pressure
ECG	Electrocardiograph
eCRF	Electronic case report form
EOS	End-of-study
EudraCT	European Union Drug Regulating Authorities Clinical Trials
IB	Investigator's Brochure
i.v.	Intravenous
ivSAF	intravenous Safety Analysis Set
LOQ	Limit of quantification
MedDRA	Medical Dictionary for Regulatory Activities
MSE	Mean squared error
PAH	Pulmonary arterial hypertension
PDs	Protocol deviations
PK	Pharmacokinetic
PKS	Pharmacokinetic Analysis Set
PR	Pulse rate

PT	Preferred Term
QTcB	QT interval corrected using Bazett's formula
QTcF	QT interval corrected using Fridericia's formula
RMP	Risk Management Plan
SAE	Serious adverse event
SAF	Safety Analysis Set
SAP	Statistical analysis plan
SAS®	Statistical Analysis Software
SBP	Systolic blood pressure
SCR	Screened Analysis Set
SD	Standard deviation
SDTM	Study data tabulation model
SE	Standard error of the mean
SOC	System organ class
$t_{\max, ss}$	Time to reach maximum plasma concentration at steady state
WHO	World Health Organization
WHO FC	WHO functional class
WHODD	WHO Drug Dictionary

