7.8.4.2 Trough concentrations

Selexipag and ACT-333679 $C_{\text{trough, ss}}$ will be listed by dose, subject, and period as well as the ratio of the periods per subject.

Summary statistics will be provided by dose, including dose normalized, and by period. Implausible $C_{\text{trough, ss}}$ values will be flagged in the listings and not included in summary statistics.

7.8.4.3 $C_{\text{max, ss}}$, $t_{\text{max, ss}}$, and $AUC_{\tau, ss}$

$C_{\text{max, ss}}$, $t_{\text{max, ss}}$, and $AUC_{\tau, ss}$ of selexipag and ACT-333679 will be listed by dose, subject, and period. The ratio of the parameters between i.v. selexipag (test treatment) and Uptravi (reference treatment) per subject will be shown, except for $t_{\text{max, ss}}$. Any values

obtained from implausible plasma concentrations of selexipag or ACT-333679 will be flagged in the listings and not included in the statistical analysis.

Summary statistics will be provided by dose and period for selexipag and ACT-333679.

Dose-normalized $C_{max, ss}$ and $AUC_{\tau, ss}$ will be listed and summarized by period as well for selexipag and ACT-333679.

$C_{max, ss}$ and $AUC_{\tau, ss}$ ratio of ACT-333679/selexipag will be listed by dose, subject, and treatment and will be summarized by dose and treatment.

The ratio of $C_{max, ss}$ and $AUC_{\tau, ss}$ of selexipag and ACT-333679 between Uptravi and i.v. selexipag, after dose normalization, within each dose level (if sufficient subjects are enrolled per level) will be estimated by fitting a mixed effect model to the data using period (i.e., treatment) as fixed, and subject as random effect to the log-transformed $C_{max, ss}$ and $AUC_{\tau, ss}$ values. The ratios of geometric means between i.v. selexipag (test treatment) and Uptravi (reference treatment) will be computed and displayed together with their 90% CI by back-transforming the period contrasts and interval boundaries of the log-transformed data. If dose-proportionality is shown within each dose, then an overall model may be considered for robustness.

The inter-subject coefficient of variation (CV_b) of $C_{max, ss}$ and $AUC_{\tau, ss}$ of selexipag and ACT-333679 will be computed by using the mean squared error (MSE) of the mixed model as an estimate of variation.

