8.2.2 Statistical methods for continuous data

8.2.2.1 *Differences between periods in $C_{max, ss}$ and $AUC_{\tau, ss}$ of selexipag/ACT-333679*

Within each dose level and after dose normalization, differences between the Utravi and i.v. selexipag periods will be analyzed by computing the geometric mean ratios of the respective period with the oral formulation as reference treatment in the denominator. This is done by fitting a mixed linear model to the log-transformed $C_{max, ss}$ and $AUC_{\tau, ss}$ values with period as fixed and subject as random effect. The Kenward-Rodgers method for calculation of degrees of freedom will be used to obtain degrees of freedom to calculate CIs. An unstructured covariance matrix will be assumed. The difference of the least squares mean and its 90% CI will be computed and transformed back to normal scale to obtain the geometric mean ratio. SAS® code similar to the code shown below will be used:

```
PROC MIXED data=<input_dataset>;
CLASS period;
MODEL log_response=period / DDFM=KR;
RANDOM intercept /subject=usubjid TYPE=UN;
ESTIMATE 'Difference i.v. - oral' period -1 1 /CL ALPHA=0.1;
RUN;
```

8.2.2.2 *CV_b in C_{max, ss} and AUC_{t, ss} of selexipag/ACT-333679*

The CV_b expressed in percent will be computed using the formula

$$CV_b [\%] = 100\sqrt{e^{S_b^2} - 1}$$

where S_b² is the MSE of the residuals from the mixed effects model described in Section 8.2.2.1.

8.2.2.3 *Dose proportionality of AUC_{t, ss} of selexipag/ACT-333679*

To assess dose proportionality of selexipag the power model approach will be used:

The power model approach specifies a relationship between the scheduled dose D of i.v. selexipag and AUC_{t, ss} of selexipag / ACT-333679 which is expressed as

$$Y_{ij} = \alpha_j' * D_i^\beta * \varepsilon'_{ij}$$

Together with α' denoting $\exp(\alpha)$ and ε'_{ij} denoting $\exp(\varepsilon'_{ij})$, logarithmizing both sides of the equation yields a linear model

$$\log(Y_{ij}) = \alpha_j + \beta \log(D_i) + \varepsilon_{ij}$$

with

Y_{ij} AUC_{τ, ss} of dose level i in subject j (i=1, ..., I), (j=1, ..., n)

α_j intercept parameter (assumed to be a random effect)

β the slope parameter

D_i size of dose level i

ε_{ij} random error term of subject j in dose level i.

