Ratio of geom. means (i.v./p.o)	xxx (xx.x, xx.x)	xxx (xx.x, xx.x)
90% CI	x.xxxx, x.xxxx	x.xxxx, x.xxxx
CV b[%]	xx.x	xx.x
CI = Confidence interval, n.e. = not estimable. p.o. = per os, b.i.d. = twice daily; i.v. = intravenous		
Geometric mean ratios were obtained by computing the anti-log of the treatment group difference of a mixed model with treatment as fixed and subject as random effect to the log-transformed data. CV_b[%] was computed using the mean squared error of residuals as a measure of variation. Values obtained from implausible plasma concentrations are not included in the analysis.		
Output: <Output name>, Produced by DATAMAP on ddMMMyyyy hh:mm (CET),		
SDTM Date: ddMMMyyyy		
Program: /<folder>/<program_name>.sas		
Page x of y		

Programming note: Display all dose levels. For dose levels not sufficiently populated to allow an estimation populate only 'n' row and show 'n.e.' for the remaining statistics.

T_PK_POW

ACT-293987

Protocol: AC-065A309

Dose proportionality of AUCtau of <selexipag/ACT-333679> after i.v. selexipag: Power model estimation

Analysis Set: Pharmacokinetic Analysis Set

n	beta	SE(beta)	90% CI
xxx	x.xxx	xx.xxxx	x.xxxx, x.xxx

CI = Confidence interval

Dose proportionality will be assumed if beta is close to 1, i.e., if the CI of beta includes 1.

Values obtained from implausible plasma concentrations are not included in the analysis.

Output: <Output name>, Produced by DATAMAP on ddMMMyyyy hh:mm (CET),

SDTM Date: ddMMMyyyy

Program: /<folder>/<program_name>.sas

Page x of y

Programming note: Produce table only if sufficient subjects are included in at least three dose levels.

T_PK_WIL

ACT-293987

Protocol: AC-065A309

Location shift analysis of tmax, ss of <selexipag/ACT-333679>

Analysis Set: Pharmacokinetic Analysis Set

n	i.v. selexipag - Uptravi Median	90% CI	p-value
xxx	x.xxx	x.xxxx, x.xxx	x.xxxx

CI = Confidence interval from a Hodges - Lehmann estimation.

p-value is derived from a Wilcoxon signed rank test.

Values obtained from implausible plasma concentrations are not included in the analysis.

Output: <Output name>, Produced by DATAMAP on ddMMMyyyy hh:mm (CET),

SDTM Date: ddMMMyyyy

Program: /<folder>/<program_name>.sas

Page x of y

[figure not shown]
F EXP

ACT-293987

Protocol: AC-065A309

Shift in selexipag dose between oral and i.v. treatment

Analysis Set: i.v. Safety Analysis Set

Output: <Output name>, Produced by DATAMAP on ddMMyyyy hh:mm (CET),

SDTM Date: ddMMyyyy

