Appendix F Document history

Summarize the main changes and rationale for changes from one approved version to the next.

Version	Effective Date	Reason
1.0	22-May-2018	New
2.0	2-Jul-2018	
Section 7.8.4: Implausible PK plasma concentrations will be identified by a PK specialist and flagged. PK parameters derived from implausible concentrations will be flagged as well. Flagged values will be listed but not included in summaries and statistical analyses.
 
Section 5.4.5.1: Added Uptravi in list of PAH-specific therapies to be displayed in the tables.
 
Section 8.2.2.4: Removed SAS code as this code will produce incorrect analysis (two-sample test / CI for median, while one-sample test / CI is appropriate).
 
Section 8.2.3.3: Added j subscript for random intercept parameter for clarification of random parameter.
 
Section 12.4.1: Added clarification that tables will be run on the SAF and only on the ivSAF if different from SAF to be consistent with Table 4.
 
T_PK_EP_SUM: Removed ratio and CVb(%), as this information is contained in T_CV_MM.
 
Listings L_EG, L_EG_QUAL, L_MH: General medical history and ECG are not collected for screen failures, thus population is changed from SCR to SAF.
 
Corrections and additions to table shells to improve readability (e.g., date/time columns added, footnotes added)

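### CV_b, defined as the inter-subject CV, is calculated from the residual variance of a model whose random intercept has already removed the between-subject variance

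*SAP*

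**What the plan says.** The SAP abbreviation list expands CV_b as "Inter-subject coefficient of variation". Protocol 10.3.5 asks for it among the summaries of Cmax,ss and AUCτ,ss ("and inter-subject coefficient of variation"), and that summary is by dose and period: "will be summarized by dose and period with arithmetic mean, geometric mean".

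The calculation is given three times, each time the same way:

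- SAP 7.8.4.3: CV_b "will be computed by using the mean squared error (MSE) of the mixed model as an estimate of variation".
- SAP 8.2.2.2: CV_b[%] = 100·sqrt(exp(S_b²) − 1), where S_b² "is the MSE of the residuals from the mixed effects model described in Section 8.2.2.1".
- SAP Appendix E, footnote to `T_PK_MM`: CV_b "was computed using the mean squared error of residuals as a measure of variation".

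The model in SAP 8.2.2.1 regresses the log PK parameter on period, with "RANDOM intercept /subject=usubjid TYPE=UN" in the code.

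Version 2.0 took CV_b out of the by-dose, by-treatment summary shell `T_PK_EP_SUM`. The document history gives the reason: "Removed ratio and CVb(%), as this information is contained in T_CV_MM". Appendix E has no shell of that name; its only mixed-model shell is `T_PK_MM`.

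**The concern.** A random subject intercept absorbs whatever a subject's oral and i.v. profiles have in common, and that shared part is the between-subject variance. What is left over measures how far the two profiles of one subject differ once the average period difference is removed. Using that remainder as S_b² answers a different question from the one the CV_b label asks.

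CV_b is specified in the protocol and appears as a row in `PK_MM_SEL` and `PK_MM_ACT`, both marked as key deliverables in SAP 12.8. Since version 2.0 these are the only places it is reported, so no correct value elsewhere would expose the error. A reader who takes the row as the spread between patients, for example when planning a later study, would be using the wrong variance component.

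There is a related gap. The protocol wants CV_b by dose and period, but `T_PK_MM` gives one value per dose level across both periods. The document history records the move, but SAP section 11 does not record the loss of the by-period figure.

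**Working it through.** The plan states no numerical CV_b, so there is no figure to reproduce. The check is algebra, then an illustration of size.

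**Algebra.** For subject i in period j, log Y_ij = μ + period_j + b_i + e_ij, with Var(b_i) = σ_b² and Var(e_ij) = σ_w². With one profile per route and complete pairs, the within-subject difference is d_i = (period difference) + e_i2 − e_i1. The term b_i cancels, so Var(d) = 2σ_w². The residual MSE equals Var(d)/2, which estimates σ_w² (plus any interaction) and contains no σ_b². `TYPE=UN` does not change this, because for a single random intercept it is a 1×1 matrix. If the intercept variance is estimated as zero, the residual becomes the pooled total variance, which is still not a between-subject component.

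**Check by REML fits of the SAP model** (n = 18, 200 simulated data sets per row):

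| True between / within CV | SAP formula | Intercept variance |
|---|---|---|
| 50% / 15% | 15.0% | 49.9% |
| 50% / 25% | 24.6% | 50.7% |
| 30% / 30% | 29.0% | 30.2% |

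The SAP formula follows the within-subject CV.

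**Illustration from the documents.** Protocol 1.2.4 gives 95% CIs for geometric mean AUC0-∞ in the absolute bioavailability study (single dose, healthy men). Assuming n = 18 for each route, the log-variance is (ln(U/L)/2 ÷ 2.110 × √18)²:

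| Analyte, route | 95% CI | Log-variance |
|---|---|---|
| Selexipag i.v. | 9.30–13.38 | 0.134 |
| Selexipag oral | 8.19–14.87 | 0.360 |
| ACT-333679 i.v. | 11.42–19.47 | 0.288 |
| ACT-333679 oral | 30.18–47.78 | 0.213 |

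`T_PK_MM` pools the routes, so I use the means: 0.247 for selexipag and 0.251 for ACT-333679. With total variance V and intra-subject correlation ρ (assumed, not in the documents), the residual variance is (1 − ρ)V and the intercept variance is ρV. Each is converted by 100·sqrt(exp(variance) − 1):

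| ρ | ACT-333679: SAP formula | ACT-333679: intercept | Selexipag: SAP formula | Selexipag: intercept |
|---|---|---|---|---|
| 0.3 | 43.8% | 27.9% | 43.4% | 27.7% |
| 0.5 | 36.5% | 36.5% | 36.2% | 36.2% |
| 0.7 | 27.9% | 43.8% | 27.7% | 43.4% |

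The figures agree only at ρ = 0.5. The SAP understates inter-subject spread above that value and overstates it below. A simulation of 20,000 paired data sets with n = 18 and the ACT-333679 variance gave means of 27.6% (SAP) and 42.9% (intercept; true 43.8%) at ρ = 0.7. At ρ = 0.3 it gave 43.0% and 25.6% (true 27.9%).

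**How well the replacement behaves.** The intercept variance is a common between-subject variance only if that variance is equal for both routes. Assume a within-subject log-variance of 0.05 (CV 22.6%) per route and perfectly correlated subject effects. Then the intercept variance is the square root of the product of the two route-specific between-subject variances:

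| Analyte | Between-subject CV, i.v. | Between-subject CV, oral | Intercept-based CV | SAP formula |
|---|---|---|---|---|
| Selexipag | 29.6% | 60.2% | 41.8% | 29.9% |
| ACT-333679 | 51.8% | 42.1% | 46.7% | 23.4% |

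Small dose levels are a second limit. At ρ = 0.7 the intercept estimate is exactly zero in 15%, 10% and 6% of simulated data sets at n = 3, 4 and 5, and its central 95% range at n = 4 is 0 to 93%. At ρ = 0.5 and n = 4 it is zero in 20%, with a range of 0 to 84%.

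**The case against.** The case for leaving this alone, or only renaming the row, has five parts.

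- *Little depends on it.* SAP 8.2 rules out confirmatory testing, and the tables are key deliverables because of the ratios and intervals. This is correct, and it limits the importance of the point.
- *The method is disclosed.* `T_PK_MM` prints only the CV_b symbol, its legend does not expand it, and its footnote names the residual mean squared error. This is also correct. But the abbreviation list, SAP 7.8.4.3 and the `T_PK_EP_SUM` legend all give CV_b the between-subject meaning, and nothing gives another. Disclosing the formula does not correct the name.
- *The spread is visible elsewhere.* CV_ln% is kept by dose level and treatment. It shows total spread, within plus between, so it softens the loss without supplying an inter-subject figure.
- *The replacement is weak in this trial.* Group A has 5 to 8 subjects over five doses (1.0 to 1.6 per level on average) and Group B has 12 to 15 over three (4 to 5 per level). Zero or very imprecise values are likely in the by-dose rows, and for selexipag the figure may match neither route. This is the strongest objection and it stands as a limit on the fix. It is not a reason to print a residual CV as an inter-subject one.
- *The sizes are only illustrative.* They come from single-dose AUC in healthy men given a different i.v. formulation, with assumed correlations, and say nothing about Cmax,ss. The mismatch itself does not depend on them.

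**Conclusion.** The concern holds. As written, the CV_b row does not estimate the quantity it is named for, and because all three descriptions agree, a programmer following the SAP will produce the wrong figure. That conclusion rests on the model structure alone. The size and direction of the discrepancy cannot be known in advance: they depend on a within/between split that the documents do not give, and on the equal-variance and n = 18 assumptions above. The consequence is confined to one descriptive row. It should be corrected, but it does not threaten the trial's conclusions.

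**What to change.** - In SAP 7.8.4.3, SAP 8.2.2.2 and the `T_PK_MM` footnote, define S_b² as the random-intercept variance from the existing `PROC MIXED` fit, giving CV_b = 100·sqrt(exp(σ²_subject) − 1).
- Keep the MSE-based figure as a second row, labelled residual (within-subject) CV, including subject-by-formulation interaction.
- State two limits in the footnote. First, the intercept variance is a common between-subject variance only if that variance is equal for both routes; with one profile per subject per route, route-specific values cannot be separated from within-subject variance. Second, in the pooled dose-normalised row it also absorbs departures from dose proportionality and differences between dose groups.
- Show n and flag zero estimates. The shell's not-estimable rule has no threshold and will not suppress them.
- Record in SAP section 11 that CV_b is one value per dose level over both periods, with CV_ln% giving total spread by period. Correct the table name in the document history.

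The cost is three text edits, a short note and one extra number from a fit already planned, with no new data or model. The price is a figure that is imprecise in small dose levels and depends on the equal-variance condition. Relabelling the present row alone would remove the wrong name, but the protocol's inter-subject CV would then go unreported, and section 11 would have to say so.

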8.2.2.4 Difference of $t_{max, ss}$ of ACT-333679

Within each dose level, difference in $t_{max, ss}$ of ACT-333679 between Periods 1 and 2 will be assessed by computing the Hodges-Lehmann estimator for shift in the median from Uptravi to i.v. selexipag. The median is computed by computing all shifts between the two periods and using the median of the shifts as an estimate. If computationally feasible, exact estimates and 90% CIs will be computed.

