Based on the previous studies QGUY/2006/NS304/-01, AC-065-101 and AC-065A201 it is known that the PK profile of selexipag and its active metabolite ACT-333679 is dose-proportional up to a single dose of 800 ug and for multiple doses of up to 1800 ug b.i.d. after oral administration.

Dose proportionality of $AUC_{\tau, ss}$ of selexipag and ACT-333679 after i.v. selexipag will be analyzed using the power model approach [Gough 1995], if at least three different dose levels with a sufficient number of subjects to compute CIs are included in the PKS. A plot of log dose versus log $AUC_{\tau, ss}$ including the slope of the estimated parameter will be displayed.

Differences in $t_{max, ss}$ of ACT-333679 between the i.v. selexipag period and the Uptravi period will be assessed within each dose level using a Wilcoxon signed rank test and displaying the median estimate and exact 90% CI of the location shift using Hodges-Lehmann estimation.

If considered appropriate, a sensitivity analysis may be conducted to evaluate the statistical impact of the plasma concentrations of selexipag or ACT-333679 that were considered implausible by the PK expert.

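### SAP 8.2.2.4 words the tmax,ss shift in a way that does not give the paired Hodges-Lehmann estimate belonging to the signed rank test planned elsewhere

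*SAP*

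**What the plan says.** SAP 8.2.2.4 compares tmax,ss of ACT-333679 between Periods 1 and 2 within each dose level. It names the method as "computing the Hodges-Lehmann estimator for shift in the median from Uptravi to i.v. selexipag" and then gives the arithmetic: "The median is computed by computing all shifts between the two periods and using the median of the shifts as an estimate". It adds: "If computationally feasible, exact estimates and 90% CIs will be computed". It mentions neither within-subject differences nor Walsh averages, and no other section describes the calculation.

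The other places that specify this comparison are paired:

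- Protocol 10.3.5: "using the Wilcoxon signed rank test providing the median differences and their 90% CI".
- SAP 7.8.4.3: "using a Wilcoxon signed rank test and displaying the median estimate and exact 90% CI of the location shift using Hodges-Lehmann estimation".
- The T_PK_WIL shell in SAP Appendix E prints the median, 90% CI and p-value in one row. Its footnotes attribute the CI to Hodges-Lehmann estimation and state: "p-value is derived from a Wilcoxon signed rank test".

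SAP Appendix F records that SAS code was taken out of 8.2.2.4 in version 2.0 because it gave a "two-sample test / CI for median, while one-sample test / CI is appropriate". That entry describes superseded code. It is used here only as evidence of what the sponsor intends.

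**The concern.** Each subject contributes one oral profile (Day 1) and one i.v. profile (Day 3), so the data are paired. The estimate and interval that invert the signed rank test are built from the averages of pairs of within-subject differences. The arithmetic in 8.2.2.4 is something else. With the code removed, that sentence is all a programmer has to work from, and two programmers could follow it and report different numbers. On the literal reading, one table row would combine an independent-samples estimate and CI with a paired p-value, and the two could disagree.

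**Working it through.** The plan states no numerical tmax shift, so there is no figure to reproduce. The check compares the candidate calculations.

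**1. Definitions.** Let x_i be the oral and y_i the i.v. tmax,ss of subject i, with d_i = y_i − x_i.

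- Two-sample Hodges-Lehmann (literal reading): median of the n² values y_j − x_i.
- Plain median (one shift per subject): median of the n values d_i.
- Paired Hodges-Lehmann (matches the signed rank test): median of the n(n+1)/2 Walsh averages (d_i + d_j)/2, i ≤ j.

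**2. Invented example on the sampling-time grid, n = 5.** Oral 1, 2, 4, 6, 8 h; i.v. 1.45, 4, 6, 8, 6 h. The differences are 0.45, 2, 2, 2, −2.

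- Two-sample: of the 25 cross-differences, 8 are negative and 4 are zero, so the 13th is 0.45 h.
- Plain median: ordered −2, 0.45, 2, 2, 2, giving 2.0 h.
- Paired: the 15 Walsh averages in order are −2, −0.775, 0, 0, 0, 0.45, 1.225 (three times), 2 (six times). The 8th is 1.225 h.

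The three rules give 0.45, 2.0 and 1.225 h, so neither reading of the sentence yields the paired estimate.

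**3. Sample size that applies.** Protocol 10.3.5, SAP 7.8.4.3 and SAP 8.2.2.4 all run this comparison within dose level (the T_PK_WIL shell shows no dose rows, but the text is explicit). SAP Table 6 has eight levels. Group A spreads 5 to 8 subjects over five levels, on average 5/5 = 1.0 to 8/5 = 1.6 each. Group B spreads 12 to 15 over three, on average 12/3 = 4 to 15/3 = 5 each.

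**4. Interval width and coverage.** The within-subject correlation ρ of tmax,ss is not in the documents, so it is an assumption, shown as a range. Simulation: bivariate normal data, no true shift, nominal 90% CIs from the exact rank-sum distribution (two-sample) and exact signed-rank distribution (paired), 10,000 trials per setting.

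| n | Two-sample width ÷ paired width, ρ = 0 / 0.3 / 0.5 / 0.8 | Two-sample coverage (%), same ρ | Paired coverage (%) |
|---|---|---|---|
| 5 | 0.73 / 0.87 / 1.01 / 1.57 | 91.1 / 94.2 / 96.6 / 99.1 | 93 to 94 |
| 6 | 0.93 / 1.11 / 1.31 / 2.01 | 90.6 / 94.8 / 96.9 / 99.4 | 90 to 91 |
| 7 | 0.88 / 1.04 / 1.23 / 1.88 | 90.2 / 94.4 / 96.9 / 99.5 | 92 to 93 |
| 8 | 0.93 / 1.11 / 1.31 / 2.00 | 91.3 / 95.5 / 97.8 / 99.7 | 92 |

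At n = 5 the low ratios partly reflect discreteness: the paired interval has exact confidence 93.75%, the two-sample interval 90.5%.

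**5. When an exact paired interval exists.** The highest confidence a signed-rank interval can reach is 1 − 2/2ⁿ. For n = 4 this is 1 − 2/16 = 87.5%; for n = 5 it is 1 − 2/32 = 93.75%. An exact 90% CI therefore needs at least 5 subjects in the dose level.

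**The case against.** A reader might infer that the plan ignores the pairing in this crossover. The documents do not support that. The protocol, SAP 7.8.4.3 and the table shell all specify the signed rank test, and Appendix F says the one-sample analysis is the appropriate one. Nor does 8.2.2.4 mention cross-subject differences or independent samples. One shift per subject is a possible reading and fits the protocol's median differences. This limits the point to one imprecise sentence. It does not rescue the sentence, because the alternative reading gives the plain median, not the Hodges-Lehmann estimate.

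A reader might also size the problem at all 18 evaluable subjects with a correlation of 0.8, where the intervals average 1.24 and 0.584 between-subject SDs, a ratio of 1.24/0.584 = 2.1. No dose level can hold 18 subjects, since Group B is capped at 15, and 0.8 is the top of an assumed range. The correlation drives the result: at 0.5 or below, the ratio for 5 to 8 subjects lies between about 0.7 and 1.3.

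It is also fair to say that little depends on this. SAP 8.2 makes all tests and CIs descriptive, SAP 12.8 does not mark the tmax tables as key deliverables, and a positive correlation makes the two-sample interval over-cover. All of that stands and sets the severity.

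**Conclusion.** The point holds as an inconsistency confined to SAP 8.2.2.4. On neither reading does its arithmetic produce the estimate that belongs to the signed rank analysis planned elsewhere. Two-sample is the likelier reading, but not the only one.

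On that reading the point estimate can differ noticeably on the same data (0.45 against 1.225 h in the invented example). The 90% CI ranges from somewhat narrower than the paired one to about twice as wide, and its coverage rises from about 90% with no correlation to over 99% at 0.8. These figures rest on an assumed correlation and continuous normal data. Real tmax values fall near seven sampling times per profile, so ties and zero differences are likely and the figures are indicative. No safety conclusion or decision in the plan depends on the result, so the impact is low.

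**What to change.** Replace the sentence in SAP 8.2.2.4 with:

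> The Hodges-Lehmann estimate is the median of the n(n+1)/2 Walsh averages of the within-subject differences (i.v. minus oral), with the exact 90% CI from the signed rank distribution where the dose level has at least 5 subjects; for smaller dose levels only the estimate and the individual differences are shown.

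This brings 8.2.2.4 into line with Protocol 10.3.5, SAP 7.8.4.3 and T_PK_WIL, and completes the correction recorded in Appendix F. It needs no new data.

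The cost is that dose levels with fewer than 5 subjects show no CI. At the planned group sizes that will include most or all Group A levels and possibly some in Group B. An exact 90% signed-rank interval cannot be formed at those sizes in any case.
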